4.5. Intervention Maneuvers in Delivery Room

Because this is an international multi-site trial, we are aware that International sites may have minor modifications of the below, all of which will be assessed for trial approval by the Steering Committee. However we do make reference below to “site clinical local practices”. If such minor variations in these will not affect the validity and integrity of the trial, they will be allowed.

At all sites where antenatal consent has been obtained, or in some sites where the local IRB has granted waiver, eligible infants (23⁰-26⁶ completed weeks GA) will be taken to a resuscitation trolley, placed in a

plastic wrap and have a SpO₂ probe attached to the right hand (NRP p.54).⁴ The infant's airway will be cleared and the infant will be commenced on mask or nasal prong CPAP at 5-7 cm H₂O and FiO₂ 0.3 via a T-piece.

A wide range of authorities have now accepted this in the peer-reviewed press as a standard procedure in 2013-2014. We have ensured that we are fully compliant with ILCOR 2010 and NRP 2011 standards, using CPAP or PEEP. We have discussed aspects of this in the study background section, and referenced the January published latest statements from the Fetus and Newborn Committee of the AAP.^{5, 6} (Appendix 7) Our NRP compliant approach is attested to in several other ways, including the approval of the DSMB that includes [name] (one of the co-founders of the AAP NRP program); the inclusion in our group of a NRP committee member ([name] from CHOP-HUP); and consistency with the Quality Program initiatives of the DR processes in HUP. (Appendix 8). For the trial, the time of birth has been set as final emergence of the infant from delivery. The time of cord clamping will be recorded. Finally, the time for the Study Intervention (see Figure 1 below) is measured from the point of the infant being placed on the resuscitation trolley (defined as time zero).

[figure not shown]
Thereafter, an infant with inadequate respiration defined as gasping or apneic; or is bradycardic defined as HR<100 bpm and not rising (as labelled in the algorithm diagram: Figure 1) will be eligible for the SAIL trial. Time in which to determine eligibility is 30 seconds, however an infant can declare himself/herself in less time. The initial 30 seconds are congruent with NRP guidelines.

Infants who are not eligible for the SAIL trial will be continued on CPAP, and all further resuscitative measures will be made according to local clinical protocols.

For infants who are eligible for the SAIL trial, the randomization envelope will be opened, and the treatment allocation will be announced to the clinical team. Thereafter, the protocol algorithm will be followed for babies who are randomized to the SI intervention. Infants who are randomized to the control arm will be treated according to local clinical protocols. (See 4.5.1 for more detail on the control arm infants).

Regarding choice of pressures: "The primary measure of adequate initial ventilation is prompt improvement in heart rate. Chest wall movement should be assessed if heart rate does not improve. The initial peak inflating pressures needed are variable and unpredictable and should be individualized to achieve an increase in heart rate or movement of the chest with each breath. Inflation pressure should be monitored; an initial inflation pressure of 20 cm H₂O may be effective, but 30 to 40 cm H₂O may be required in some term babies without spontaneous ventilation if circumstances preclude the use of pressure monitoring, the minimal inflation required to achieve an increase in heart rate should be used." The choice of pressure is discussed further below under section 4.5.2.

Figure 1: The overall schema for eligible versus non-eligible infants

4.5.1. Control Arm Infants

Infants randomized to this arm will follow standard NRP guidelines. While starting on CPAP, this may include the provision of T-piece resuscitator (positive pressure) ventilation with peak pressures set initially at 20 cm H₂O for 15 seconds, and if needed subsequently, increased to peak pressure of 25 H₂O cm, or as local clinical practices allow. Corrections by MR. SOPA are to be applied as recommended by NRP guidelines. These are discussed in fuller detail below under 4.5.2.

4.5.2. Intervention Arm Infants

All respiratory support is to be administered via the T-piece resuscitator and either face mask, nasopharyngeal tube (NPT) or a shortened endotracheal tube placed as an NPT. The Mountain trial has reported that there is no difference in interface. ([Appendix 9](#)) SI will be delivered via T-piece resuscitator, as this device has been shown to be the only one capable of effective delivery of CPAP and SI (Hussey SG 2004, Klingerberg C 2011).

The choice of initial pressure for the SI is based on pathophysiology, literature, local practice or other and available data. While animal studies suggest that inflation pressures as high as 35 cm H₂O are needed in animals with no spontaneous effort and no antenatal steroids⁷⁻¹¹, human trials suggest that when the lungs are partially aerated as a result of the infant's respiratory effort, pressures as low as 20 cm H₂O may be sufficient. A single SI with a pressure of 25 cm H₂O was used in a recent cohort study¹² without apparent adverse effects. Escalating SI pressure ranging from 20 to 30 cm H₂O for up to 3 SIs was used by the other two studies. The first reported that 67% of infants required 25 cm and 8% received SI of 30 cm H₂O.¹³ SIs of 20 cm H₂O were adequate in 60% of infant in the other trial, while 40% of infants required 25 cm H₂O and of those, the majority had an inadequate response and required intubation¹⁴. At that center, SI of up to 30 cm H₂O is now used as part of standard DR care.

Thus, eligible infants will be given the first SI using pressure of 20 cm H₂O. An assessment for respiratory effort and heart rate will be made. Infants with adequate respiratory effort and heart rate above 100 bpm will continue on CPAP as study intervention has ended for these infants and they revert to standard NRP procedures.

For those infants following the first SI who remain without adequate respiratory effort, a second SI using a pressure of 25 cm H₂O for 15 seconds will be delivered. In the interval between the first SI and the second SI, the team will follow standard NRP procedures as described in the next paragraph (MR SOPA). Decisions about adequacy of the SI will be based on infant's response as judged by improving HR, respiratory effort and SPO₂.

During this period between SIs, as per NRP recommendations, adjustments can be made to ensure no residual lack of seal or obstruction is impeding the infant, resuscitation will proceed according to the first four steps of the "MR. SOPA rule". (i.e. Mask Readjustment; Suction airway; Open mouth.) In both the NRP algorithm as well as the SI algorithm, MR. SOPA is incorporated in the step outlined as "take corrective ventilation steps". Last, if the infant is eligible for a second SI, the clinician will

ensure airway patency and deliver the second SI with a pressure 5 cm higher than the initial pressure. This step is in accordance with the P step of MR. SOPA.

[figure not shown]
The final 'A' in MR. SOPA stands for Airway. There will be rare situations where the clinician must respond with intubation immediately – such infants will be also randomized into an SI or standard arm. While these infants data will be pooled, it will also be treated separately in a sub-group analysis. At any point in the algorithm, if the HR is < 60 and not increasing, PPV may be given with rate in accordance with NRP and peak inspiratory pressure equal to the SI that would otherwise be performed. Observation after a 15 second period will assess whether there is an improving heart rate. If the heart rate improves to >60, the algorithm will be resumed from the point of departure.

Throughout the entire period, cardiac compressions will start if HR remains < 60 despite effective respiratory support for > 30 seconds.

Finally, Figure 1 shows two red lines. The first is the initial assessment point which by 30 seconds must be completed as according to NRP. However the second dotted redline indicates that by 5 minutes there may have been a progression towards intubation. This decision point may be reached by 2 minutes or even before.

The modified but NRP compatible procedures are shown for the SI arm in more detail in Figure 2.

Figure 2: Algorithm For infants In Intervention arm directly compared to the NRP algorithm.

Control Arm: NRP

Sustained Inflation Arm

The potential risks of this maneuver are described in Section 8 and in the adverse event reporting section. The main risk anticipated is the potential for a pneumothorax. However, we do note that not only has an excess risk not been seen in the available randomized data to date, but the pressures stipulated in the algorithm are within the ranges of those recommended by NRP for conventional resuscitation. The DCC will monitor carefully for potential excess risk, and some of the secondary objectives are also part of the materials in adverse event reporting and will be transmitted at appropriate intervals to the DSMC.

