5.1.1. Potential Confounders and Strategy to Limit Impact

Severity of initial illness: Randomization should achieve balance at baseline. Adjustment for SNAPPE scores on admission to the NICU will be performed during the analysis of the primary outcome.

Site Variation: Randomization will be stratified by site.

General respiratory management in the DR and beyond: Local unit protocols will be followed with respect to aspects of respiratory support not specifically addressed in the study interventions. In general, after initial resuscitation, CPAP will be the initial mode of respiratory support in reasonably vigorous infants. Intubation will be reserved for infants who remain apneic, are without adequate respiratory effort, or have persistent bradycardia. Surfactant for RDS prophylaxis will not be given in the DR prior to SI (if so randomized), even if the infant is intubated. Caffeine will be administered to infants if needed for respiratory support.

Extubation and intubation guidelines: Continued need for mechanical ventilation is associated with BPD. We adopt a uniform guideline to intubation and extubation, though clinical circumstances may preclude strict adherence to guidelines at all times. There is no consensus about weaning babies from mechanical ventilation. Therefore, the proposed extubation guidelines are based on consensus and criteria used in several current and recent large clinical trials. On a daily basis the infant will be assessed for ability to wean from ventilation. We will strongly encourage extubation to be attempted within 24 hours after meeting all following criteria: $PCO_2 \leq 55$ mm Hg and a $pH \geq 7.25$, FiO_2 of ≤ 0.4 with an SpO_2 of $\geq 88\%$ or higher, mean airway pressure of ≤ 8 cm of water, and hemodynamic stability and without evidence of clinically significant patent ductus arteriosus. All infants will have received caffeine prior to an extubation attempt. Extubation may be attempted at higher settings at the discretion of the clinical team. Following extubation all infants should be placed on nasal CPAP or NIPPV, not on nasal cannula or oxihood. In unplanned extubations, the infant will be given an opportunity to remain extubated, if heart rate and oxygen saturations are maintained without excessively high FiO_2 or work of breathing. Extubation will be considered successful if the infant remains extubated for at least 48 hours. Reintubation will be at the discretion of the clinical team managing the infant.

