2.3.2 Secondary Efficacy Endpoints

The secondary efficacy endpoints (and associated secondary aim) are defined below. Endpoints considered adverse events / safety endpoints are given in Section 2.3.3. The timing of evaluation of each endpoint is given in bolded font.

Delivery Room (DR):

- 1. Heart rate in the DR (SA1a)
 Categorical variable with 3 levels: <60, 60-100, >100
- 2. Type of respiratory support (CPAP, PPV) on departure from DR (SA1b)
- 3. Fraction of Inspired Oxygen (FiO₂) on departure from DR (SA1b)
- 4. Pressure-volume characteristics in the DR (at several but not all sites) (SA4)
- 5. Need for intubation in DR (SA3)

First 48 hours of life:

- 6. Use of inotropes (SA1c)
 - Any use within first 48 hours of life
- 7. Pneumothorax (SA1d, SA8)

Source documentation needed for adjudicated yes/no variable

- 8. Need for new chest drains (SA1de)
 - Calculated as an increase in the number of chest drains recorded hourly.
- 9. Oxygen requirement of $Fi0_2 \ge 40\%$ for 2 hours or more (SA1g)
- 10. Highest FiO₂ level recorded during the first 48 hours post DR (SA1h)
- 11. Area under the hourly FiO₂ curve (SA6)
- 12. Need for intubation in DR or during first 48 hours of life (SA3)

First 7 days of life:

13. Death or need for positive pressure ventilation at 7 days (SA5)

First 10 days of life:

14. Need for new chest drains (SA1de)

Calculated as an increase in the number of chest drains recorded hourly for the first 48 hours, and then daily up to 10 days of life.

15. Duration of any chest drain (SA1f)

Calculated as the amount of time the number of chest drains is >0. Since this will be measured hourly for 48 hours and then daily, the finest level possible will be calculated for each infant and then the data will be examined to determine the scale for analysis.

- 16. Highest FiO₂ level recorded from 48 hours to 10 days of life (SA6)
- 17. Air leak (SA8)

Defined as radiographic evidence of pneumothorax, pulmonary interstitial emphysema (PIE) or pneumopericardium.

36 weeks PMA:

- 18. Death (SA2)
- 19. BPD defined using a standardized oxygen reduction test (SA2)

Discharge:

- 20. Retinopathy of prematurity (ROP) stage 3 or greater requiring treatment (SA10)
- 21. Death in hospital (SA11)
- 22. Survival to discharge home without BPD, retinopathy of prematurity (grades 3 & 4), or significant brain abnormalities on head ultrasound (SA7)
- 23. Length of hospital stay in days (SA13)
- 24. Use of postnatal steroids for treatment of BPD (SA12)

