10. APPENDIX B: DRAFT STUDY REPORT TABLES

The following are examples of some of the tables that may be included in final report for this clinical trial. Selected tables may also be used for reporting the results of the interim analyses. Although the exact content and format may change, an attempt has been made to summarize the most important population, safety, and efficacy data.

Table 1. Summary of Baseline Demographic Characteristics by Intervention Group

		A		В	T	otal	p-value
Number of Subjects	~n		~n		~n		
Clinical Site							
University of Pennsylvania	n	(%)	n	(%)	n	(%)	n/a
University of Melbourne	n	(%)	n	(%)	n	(%)	
etc.	n	(%)	n	(%)	n	(%)	
Consenting Procedure Used							
Antenatal	n	(%)	n	(%)	n	(%)	0.xx
Deferred	n	(%)	n	(%)	n	(%)	
Sex							
Male	n	(%)	n	(%)	n	(%)	0.xx
Female	n	(%)	n	(%)	n	(%)	
Race							
White/Caucasian	n	(%)	n	(%)	n	(%)	
Black/African-American	n	(%)	n	(%)	n	(%)	
etc.	n	(%)	n	(%)	n	(%)	
Gestational Age							
Median	X	X.X	X	X.X	Х	X.X	0.xx
Range	XX	to xx	XX	to xx	XX	to xx	
Maternal Age							
Median	X	X.X	X	X.X	Х	X.X	0.xx
Range	XX	to xx	XX	to xx	XX	to xx	
Maternal Gravidity							
Median	X	X.X	X	X.X	Х	X.X	0.xx
Range	XX	to xx	XX	to xx	XX	to xx	

Table 2. Summary of Baseline Clinical Characteristics by Intervention Group

		A		В	To	otal	p-value
Number of Subjects		~n		~n		~n	
Exposure to Antenatal Steroids							
No	n	(%)	n	(%)	n	(%)	0.xx
Yes	n	(%)	n	(%)	n	(%)	
Type of Antenatal Steroids (only in subset with exposure)							
	n	(%)	n	(%)	n	(%)	0.xx
	n	(%)	n	(%)	n	(%)	
Exposure to Medications to Prolong Pregnancy							
No	n	(%)	n	(%)	n	(%)	0.xx
Yes	n	(%)	n	(%)	n	(%)	
Placental Abruption							
No	n	(%)	n	(%)	n	(%)	0.xx
Yes	n	(%)	n	(%)	n	(%)	
Chorioamnionitis							
No	n	(%)	n	(%)	n	(%)	0.xx
Yes	n	(%)	n	(%)	n	(%)	
Membranes Rupture ≥ 24 hours before Delivery							
No	n	(%)	n	(%)	n	(%)	0.xx
Yes	n	(%)	n	(%)	n	(%)	
Mode of Delivery							
Vaginal	n	(%)	n	(%)	n	(%)	0.xx
C-Section	n	(%)	n	(%)	n	(%)	
Route of Intervention Administration							
Facemask	n	(%)	n	(%)	n	(%)	0.xx
Nasopharyngeal Tube	n	(%)	n	(%)	n	(%)	
		• /		. ,		. /	

Table 3: Screening and Eligibility

	Total
Total Infants Screened	~n
Eligible	n (%)
Ineligible	n (%)
Reasons for exclusion / ineligible:	
Baby was active, crying, HR>100bpm	n (%)
Considered non-viable	n (%)
Major anomaly (ies)	n (%)
Mother unable to consent	n = (%)
Parent refused consent	n (%)
Total Randomized	~n
Completed Study	n (%)
Completed 36 week PMA assessment	n = (%)
Completed first month of life	n (%)

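### The planned subgroup of infants needing immediate intubation has no visible record of that judgement before allocation is revealed, so as written it rests on a post-allocation variable that is also an endpoint

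*Protocol*

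**What the plan says.** Protocol 4.5.2 states: "There will be rare situations where the clinician must respond with intubation immediately". It continues that "such infants will be also randomized into an SI or standard arm", and then: "While these infants data will be pooled, it will also be treated separately in a sub-group analysis". It gives no criterion, time limit or recording step for this judgement.

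Protocol 4.6 opens the envelope once the infant is born and judged to need help with breathing. For an eligible infant, Protocol 4.5 says "the randomization envelope will be opened, and the treatment allocation will be announced to the clinical team". Protocol 4.3 accepts that the intervention is unblinded.

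Intubation in the delivery room is also an outcome. It is item 2c of the secondary aims in Protocol 2.2 and endpoint 5 in SAP 2.3.2 ("Need for intubation in DR (SA3").

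The subgroup list in SAP 5.4.1 names consent procedure, route of treatment and enrolment date. It neither names nor defines the immediate-intubation subgroup.

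**The concern.** A subgroup keeps the protection of randomisation only if membership is settled without knowledge of the arm. Here the team hears the allocation, and nothing visible shows that the need for immediate intubation was fixed beforehand. Suppose staff in one arm tend to try the allocated manoeuvre first, while staff in the other intubate sooner. The two halves of the subgroup would then hold infants of different severity, and a difference in death or BPD could appear with no treatment effect behind it.

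What is at stake is the reading of one subgroup table. It concerns some of the sickest infants in the trial, so an apparent harm or benefit there could be taken seriously despite its weak basis.

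**Working it through.** The plan states no figure on this point. The first check is therefore textual and the second is an illustration of size.

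**1. When is membership fixed?**

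- *Trigger for opening (Protocol 4.5, 4.6):* need for respiratory support. Need for immediate intubation is not part of it.
- *Place of the rule (Protocol 4.5.2):* under the last letter of MR. SOPA, among the corrective steps described for the period after a first inflation. The same section separates the 30-second assessment line in Figure 1 from a later line for progression towards intubation, at up to 5 minutes and possibly 2 minutes or sooner.
- *Eligibility and Randomization form (Protocol 5):* eligibility, date and time of randomisation, and allocation. No item for this judgement.
- *Delivery Room form (Protocol 5):* intubation as a procedure performed, with the data to be completed within 48 hours. No time of decision or of intubation is named.

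On the visible plan, the only variable from which membership can be taken is delivery-room intubation. It is recorded after open-label allocation and is itself an endpoint.

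**2. How large could the bias be?**

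The only input from the documents is the 65% control risk (Protocol 6.1.1). Everything else is assumed. There is no treatment effect, and differences are SI minus control.

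*Severity model.* Severity S is standard normal and logit(risk) = a + b·S, with b = 0.5 or 1.0 and a set so that mean risk is 65%. The label goes to the top share q of a score 0.7·S + √(1 − 0.7²)·noise, so label and severity correlate at 0.7. The model was run on 2,000,000 simulated infants.

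| Labelled, control | Labelled, SI | Difference, b = 0.5 | Difference, b = 1.0 |
|---|---|---|---|
| 5% | 5% | 0 | 0 |
| 10% | 5% | 77.4% to 79.2%: +1.8 | 85.5% to 87.9%: +2.4 |
| 10% | 2% | 77.4% to 81.2%: +3.8 | 85.5% to 90.3%: +4.8 |
| 20% | 5% | +4.1 | +5.6 |
| 5% | 10% | −1.8 | −2.4 |

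Swapping the arms reverses the sign. Equal labelling gives no bias.

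*Strongest assumption.* Label 10% of controls (risk 85%), but in the SI arm only the sicker half of such infants (5%, risk 95%). The subgroup reads 95% against 85%, a spurious 10 points. The remaining infants have (0.65 − 0.10 × 0.85)/0.90 = 62.8% in control and (0.65 − 0.05 × 0.95)/0.95 = 63.4% in SI. This implies a risk of 2 × 85% − 95% = 75% in the less sick half, a 20-point gap within one severe group.

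*Precision.* If the subgroup is 2% to 10% of 300 per arm (6 to 30 infants; assumed), power for the plan's 65% against 52.5% is Φ[(δ√n − 1.96·√(2p̄q̄)) / √(p₁q₁ + p₂q₂)]. Here δ = 0.125, p̄ = 0.5875, √(2p̄q̄) = 0.696 and √(p₁q₁ + p₂q₂) = 0.691.

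- n = 6: Φ(−1.53) = 6%
- n = 30: Φ(−0.98) = 16%

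The matching sample-size formula at two-sided α = 0.038 and 80% power returns the plan's 263 per arm.

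**The case against.** The strongest reply is about timing. Protocol 4.5.2 can be read as the need being recognised first and randomisation following, and the word for immediacy suggests a departure from the stepwise sequence. Protocol 5.1.1, where prophylactic surfactant "will not be given in the DR prior to SI (if so randomized), even if the infant is intubated", also fits intubation before the inflation. A reader might infer that the documents show the decision being made after allocation. They do not. What stands is narrower: even if the judgement comes first, no visible item preserves it for the analysis.

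Second, Figures 1 and 2 and the operating manual were not available for this check, and the form table in Protocol 5 is a summary. A recording step may exist there. If it does, the protocol and SAP should cite it.

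Third, the consequences are limited. The infants stay in the pooled analysis by allocation, the situation is described as rare, and both documents treat subgroup work as hypothesis-generating. All of that stands. It lowers the priority, but low precision does not remove bias.

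Fourth, a reader might infer a conflict between protocol and SAP from the missing subgroup, or an error from the route rows ("Route of Intervention Administration") in SAP Appendix B, Table 2, which offer only facemask and nasopharyngeal tube. Neither inference is supported. The subgroup list is introduced as examples of particular interest, and the protocol's own list in 6.1.2.2 omits the subgroup too. The tables are drafts whose content may change.

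**Conclusion.** The concern holds in a limited form. The protocol promises a subgroup analysis, but on the visible text and forms membership can only come from an intubation variable recorded after open-label allocation, which is also an endpoint. The comparison is biased if labelling differs by arm. The documents give no evidence that it will, and no frequency beyond rare.

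The size is therefore unknown. Under the assumed severity model it is roughly 2 to 6 points in either direction. The 10-point figure needs the strongest assumption; the severity model gives 1.8 to 2.4 points for the same 10% against 5% split. It would be wrong to read 10 points as the expected bias, or to read the bias as always running against SI.

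A reader might also infer that the primary result is compromised. It is not: the pooled intention-to-treat comparison does not depend on this label.

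**What to change.** Add one yes/no item to the Eligibility and Randomization form, settled before the envelope is opened: *immediate intubation judged necessary*. In SAP 5.4.1, list the subgroup and define it by that item alone. Keep every infant in the pooled primary analysis. Intubations decided after opening should count only as outcomes, not as subgroup membership.

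The cost is a tick-box on a form already assigned to the first 30 seconds, plus a few lines of protocol and SAP text. The downside is one more item to settle in that window. If it is completed from memory afterwards, the bias returns. If it is not workable in the time available, label the analysis post-randomisation and descriptive, and draw no between-arm treatment-effect inference from it.

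Separately, Protocol 4.5.2 routes all respiratory support in the SI arm through "either face mask, nasopharyngeal tube (NPT) or a shortened endotracheal tube placed as an NPT", while 4.5.2 and 5.1.1 elsewhere foresee intubated infants in that arm. The investigators should reconcile these passages for infants who are already intubated. No clinical rule is proposed here.
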